This investigation addresses a number of novel and important issues. First and foremost there has never been a longer-term randomized clinical trial, to our knowledge, that has attempted to improve relapse-risk based on a priori knowledge of AW history. This has **enormous clinical importance for alcoholics that might be biologically (perhaps genetically) prone to experience AW symptoms (a high relapse-risk group)**. Second, this study is novel in that it could begin to **aid in understanding neurobiological underpinnings of relapse in those with AW and link this to medication response** – thereby providing both face and predictive validity for these biologic differences. Furthermore, the **exploration of how several genes in these key biological systems which have been previously linked to alcohol dependence, or alcohol effects, might interact with brain chemical differences and medication efficacy** is highly novel and points to an enhanced “personalized medicine” approach. Finally, this highly translational approach **could add significant information linking clinical and basic science findings**.

Approach

General Design of the Study: *Over a 39-month enrollment period 190 subjects will be recruited from both specific research advertisement and from our clinical program. After a minimum of 3 and maximum of 7 days of abstinence, 90 subjects (about 50% of those screened) who meet DSM-5 criteria for both alcohol use disorder AND a history of AWS (DSM-5 AW Item positive) with CIWA-Ar scores < 10, will receive gabapentin (N=45) or matching placebo (N=45) for 16 weeks while receiving medical management (MM). Outcome will be assessed during this 16-week treatment period and again at one month and three months after the treatment period. Inclusion/exclusion criteria as follows are based on previous studies but modified to focus on AW symptoms.*

Inclusion Criteria:

- Ages 18-70 meeting criteria for primary alcohol use disorder based on current DSM-5 criteria and consuming, on average, 5 standard drinks per day for men and 4 drinks per day for women in the past 30 days, *who also meet a history of DSM-5 alcohol withdrawal criteria*.
- Must be able to maintain sobriety for a minimum of 3 days as determined by self-report, urinary EtG, and breathalyzer measurements

Exclusion Criteria:

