- Meets DSM-5 criteria for any other psychoactive moderate to severe substance use disorder except nicotine use disorder. Any mild substance use disorder, except marijuana and nicotine, in the last 30 days by subject report and urine drug screen
- Meets DSM-5 criteria for current axis I disorders of major depression, panic disorder, obsessive-compulsive disorder, post-traumatic stress syndrome, bipolar affective disorder, schizophrenia, or eating disorder or any other psychotic disorder or neurocognitive disorder
- Has current suicidal ideation or homicidal ideation.
- Need for maintenance or acute treatment with any psychoactive medication including anti-seizure medications. Use of alcohol medications (naltrexone, topiramate, acamprosate, disulfiram) in last 30 days.
- Clinically significant medical problems including hepatocellular disease indicated by elevations of ALT and AST of at least 3.0 times normal at screening and/or after 7 days abstinence
- Sexually active females of child-bearing potential who are pregnant (by urine HCG), nursing, or not using a reliable form of birth control
- Pending charges for a violent crime (not including DUI offenses).
- Does not have a stable living situation
- Has taken gabapentin in the last month or experienced adverse effects from it at any time
- *Has a CIWA-Ar score of 10 or more during assessment or history of AW seizures or DT's*
- For ¹H-MRS, 1) metal in, or near, head 2) significant claustrophobia or 3) inability to lie still for up to 1 hour

After initial phone screening, further in person screening will occur after signed informed consent (if their breathalyzer reading is zero). A urine drug screen will be obtained during the initial assessment day, and on all screening days a breathalyzer measurement will be done. Subjects will have their blood drawn for a general health screen, liver function tests, gamma glutamyl-transferase (GGT) and carbohydrate deficient transferrin (%dCDT). Also, on the first day, the DSM-5 criteria for alcohol use disorder will be assessed with special attention to the criteria for AW. Historical symptoms of AW based on SCID interview will be recorded and a CIWA-Ar will be done. The CIWA-Ar will be repeated at each screening visit. Those that meet criteria for the DSM-5 AW item (current or historical) will be included – we expect about 55% of screened subjects to meet

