BDI/BAS		X			X		X		X		X		X	X	
SCID-FULL		X													
ALCOHOL DEP. SCALE		X										X	X	X	
ASI		X										X	X	X	
RAND SF-36		X										X	X	X	
FAMILY HX-FROM ASI		X													
DRINC*		X										X	X	X	
MED. HX AND PHYSICAL		X													
BIOLOGICAL TESTS															
HEALTH PANEL	X						X					X			
LIVER FUNCTION TESTS	X				X		X		X		X		X	X	
CBC	X						X				X				
DRUG SCREEN	X						X				X				
%dCDT	X				X		X		X		X		X	X	
Urinary EtG		X													
URINE RIBOFLAVIN	X	X		X	X	X	X	X	X	X	X				
PREGNANCY TEST	X		AS NEEDED -----												
DNA COLLECTION	X														
Mass Spectroscopy Imaging		X		X											
MEDICAL MANAGEMENT															
GROUP A	BASELINE-----		PLACEBO -----									-FOLLOWUP-----			
GROUP B	BASELINE-----		GABAPENTIN UP TO 1200 MG DAILY--									-FOLLOWUP-----			
The following assessments are for inclusion/exclusion criteria: SCID, CIWA-Ar, Form 90, LFT's, CBC, DRUG SCREEN, PREGNANCY TEST, EtG, HX AND PHYSICAL. The following for subject characterization: ASI, DrInC, ADS, FAM-HX, DNA; and the following for efficacy (TLFB, OCDS, RAND SF-36, PSQ index, POMS, GGT, %dCDT, RIBOFLAVIN) or safety (SAFTEE interview and BLOOD TESTS).															

A Survey System Data Capture program that reduces the risk of data entry errors by utilizing a tablet PC (rather than paper) and stylus (rather than pen) will be used for data collection of questionnaires and interviews. The system ensures that all necessary items on a questionnaire must be answered, as "business rules" can be implemented, which alert the participant to complete the missing item before the next questionnaire is administered. Data collected using the Survey System data capture program are easily exported into SPSS data files, and exporting of data will occur immediately following each participant's visit and checked for completeness, outliers, and adequacy of transfer. SPSS data files are backed-up daily.

Gabapentin Dosing: Our group has experience with the use of gabapentin, as detailed in the background section, in alcohol withdrawal studies (Myrick, 2007) and clinical trials (Anton, 2009; Anton, 2011). In our

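### The qualifier on sexual activity governs the pregnancy and nursing exclusions as well as the birth-control one, so read literally the bullet does not exclude a nursing (or pregnant) woman classed as not sexually active

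*Combined protocol and SAP*

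**What the plan says.** The only exclusion for pregnancy or nursing is one bullet under Exclusion Criteria in the Approach section: "Sexually active females of child-bearing potential who are pregnant (by urine HCG), nursing, or not using a reliable form of birth control".

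The trial enrols women. The Inclusion Criteria cover ages 18 to 70 and set a drinking threshold for each sex: "consuming, on average, 5 standard drinks per day for men and 4 drinks per day for women in the past 30 days". They do not mention pregnancy or nursing.

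Table 1 schedules a pregnancy test at baseline and afterwards as needed. Its footnote sorts the assessments by purpose and puts this test in the eligibility group: "The following assessments are for inclusion/exclusion criteria: SCID, CIWA-Ar, Form 90, LFT's, CBC, DRUG SCREEN, PREGNANCY TEST, EtG, HX AND PHYSICAL". Neither the table nor the footnote limits the test to sexually active women, and neither says what follows from a positive result.

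Under General Design of the Study, those enrolled "will receive gabapentin (N=45) or matching placebo (N=45) for 16 weeks while receiving medical management (MM").

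**The concern.** The subject of the sentence is "Sexually active females of child-bearing potential", and everything after it describes members of that group. Pregnancy and nursing therefore exclude a woman only if she is also sexually active. That restriction makes sense for contraception, where a woman who is not sexually active may have no need of it. It has no evident purpose for a woman who is already pregnant or nursing.

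Screening staff apply this sentence as a rule. One who follows the words and one who follows the presumed intent could decide differently about the same woman. The literal decision could expose a nursing infant or a fetus to study drug, which with equal allocation is gabapentin for half of those enrolled and placebo for the other half.

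**Working it through.** No arithmetic applies, and the plan has no figure to reproduce. The check is a logical reading of the bullet, followed by a search for another provision that covers the same cases.

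**Step 1: the bullet as a condition.** Let A = sexually active, C = of child-bearing potential, P = pregnant by urine HCG, N = nursing, B = no reliable birth control. As written, a woman is excluded if

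A and C and (P or N or B).

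**Step 2: apply it to women of child-bearing potential (C true).**

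| Condition present | Sexually active | Not sexually active |
|---|---|---|
| Pregnant | excluded | not excluded |
| Nursing | excluded | not excluded |
| No reliable birth control | excluded | not excluded |

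In the right-hand column, only the last row is a result that the qualifier evidently serves. The first two rows are the gap.

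**Step 3: look for another provision that closes the gap.**

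- *Inclusion Criteria:* silent on pregnancy and nursing.
- *Other exclusions:* the nearest is the general medical one, "Clinically significant medical problems including hepatocellular disease indicated by elevations of ALT and AST of at least 3.0 times normal". It names neither condition.
- *Screening text after the exclusion list:* describes breathalyzer, urine and blood tests, CIWA-Ar, SCID, history and physical exam. It mentions neither a pregnancy test nor nursing.
- *Gabapentin Dosing:* covers tolerability, titration and suicidal ideation, and neither of these conditions.
- *Table 1 and footnote:* schedule a pregnancy test for eligibility. They contain no decision rule and do not mention nursing.

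**Step 4: compare the two gap cases.** A pregnancy would probably be detected, because a baseline test is scheduled and listed for eligibility. What is missing is an unqualified rule for acting on the result. Nursing has no scheduled test and appears nowhere else. A history might bring it out, but the only instruction on what to do with that information is the qualified bullet.

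**The case against.** The strongest reply is that the intent is plain. The bullet names urine HCG and Table 1 tests for pregnancy without condition. To enrol a pregnant woman, staff would have to hold a positive eligibility test and set it aside on a strained reading of the sentence. Nothing in the documents suggests that they would. *Sexually active* is also undefined: there is no look-back period and no statement that it rests on self-report. A positive HCG is ordinarily evidence of recent sexual activity, so staff could treat the pregnancy itself as meeting the qualifier. These arguments largely answer the pregnancy case. They do little for nursing, which no test detects and which need not imply recent sexual activity.

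Two stronger readings are tempting, and the documents support neither.

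- A reader might infer that Table 1 contradicts the bullet, so that a positive test fails eligibility in one place and not in the other. It does not. The footnote lists which assessments serve eligibility and gives no threshold or consequence for any of them. The rule stands in the bullet alone.
- A reader might want to say how many of the 90 participants could be affected. The documents give no number or rate of pregnant or nursing women among those screened, and none for how they would be classed on sexual activity. Any count would be a guess.

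It would also overstate the point to say that the plan makes such women eligible. They are not excluded by this bullet; every other criterion would still have to be met.

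**Conclusion.** The point holds as a drafting defect in an operative eligibility rule. A misplaced qualifier leaves a nursing woman, and on a literal reading a pregnant one, outside the exclusion if she is classed as not sexually active. The nursing gap carries most of the weight, because the bullet is the only safeguard; the pregnancy gap is largely covered in practice.

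The size cannot be stated as a number. The conclusion rests on the ordinary grammar of the sentence and on the absence of any other pregnancy or nursing provision in the documents supplied. It does not assume that any such woman would in fact be enrolled, and there is no sign that the sponsor meant to admit one. Nothing in sample size, power or the primary analysis depends on it. It is a minor point that is worth correcting because the correction is so small.

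**What to change.** Reword the bullet so that the pregnancy and nursing conditions stand alone, and so that child-bearing potential and sexual activity qualify only the birth-control condition. For example, split it in two: (a) pregnant by urine HCG, or nursing; (b) of child-bearing potential, sexually active and without a reliable method of contraception. The sponsor should confirm that this is what was meant; the unconditional pregnancy test already listed for eligibility in Table 1 is consistent with it.

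The cost is one sentence in the Exclusion Criteria. The baseline pregnancy test is already scheduled, and nursing status can be asked at the history already planned before randomization. No visit, assay or analysis changes.

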As noted previously, gabapentin is thought to reduce brain glutamate (Cunningham, 2004; Errante & Petroff, 2003) and increase brain GABA (Loscher, 1991) perhaps through its action on voltage sensitive $CA(2+)$ channels (Quintero, 2011; Sills, 2006) thereby potentially rebalancing the dysregulated GABA/glutamate tone evident at the cessation of drinking. *We have the opportunity to examine this issue as it relates change during early abstinence, relapse prediction, and gabapentin effectiveness.* We can do this based on recent advances in magnetic resonance spectroscopy (1H -MRS) that has allowed in vivo measurement of both of these neurotransmitters in humans. Given the recent recruitment of a world-renowned brain-imaging physicist, [name], to our Institution and based on our pilot method development data, we are confident that we can apply (1H -MRS) to this aim. Please see the approach-methods section for our pilot work using 1H -MRS to measure brain glutamate and GABA levels.

Previous 1H -MRS studies have generally supported brain glutamate and GABA level disturbances in individuals with alcohol dependence (AD) but timing of measurement in relationship to alcohol use and abstinence as well as alcohol severity, brain area of measurement, sample size, smoking, sex, and recent use of benzodiazepines for detoxification all might influence results. The preponderance of studies have supported elevated cerebrospinal fluid (Tsai, 1998) and anterior cingulate/prefrontal (Frischknecht, 2010; Hermann, 2011; Lee, 2007; Thoma, 2011) glutamate/glutamine levels in recently drinking AD's relative to controls, while several showed changes over time during early abstinence (Frischknecht, 2010; Hermann, 2011; Mon, 2012; Umhau, 2010). Several others showed no differences between AD and controls, perhaps because measurements were made in the occipital lobe, had small sample sizes, used older measurement methods or sampled later in abstinence (Behar, 1999; Mason, 2006). Also, ACC glutamate levels were associated with cognitive function during early abstinence (Lee, 2007) and craving after detoxification (Bauer et al, 2013). Most germane to this proposal, Umhau (2010) reported that glutamate increased during early abstinence (consistent with Mon, 2012) and that this increase was suppressed by acamprosate treatment, a drug approved by the FDA for relapse prevention and thought to stabilize glutamate function.

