these criteria based on data from our 4 recent clinical trials containing a total of almost 400 subjects. A CIWA-Ar score of 10 or more at any time during screening (5% of AW SCID positives based on recent studies), indicating the need for a more aggressive medical detoxification (Mayo-Smith, 1997; Saitz, 1998), will be exclusionary and we will refer the subject for clinical care and/or provide short-term benzodiazepine (lorazepam) until further care can be arranged. We feel that this is a fair compromise between appropriate subject selection, ethical treatment of subjects, and scientific integrity (referring individuals for clinical care and not including participants taking benzodiazepines which might compromise efficacy measures, GABA/glutamate levels, or interpretation of gabapentin response).

Study subjects will be asked to come into the clinic at least 2 times prior to randomization (with breathalyzer, CIWA-Ar, and urine EtG collected). During this time a full SCID, other questionnaires, a physical history and exam will be done. Subjects who maintain sobriety for at least 3 days will undergo a mass spectroscopy scan (¹H-MRS for glutamate and GABA) immediately before receiving the first MM session and first dose of study medication. We chose 3 days of sobriety based on our past results from previous work (Anton 2011) but not too long (no longer than 7 days) as to effect potential gabapentin efficacy measurement and/or GABA/glutamate levels. If they cannot maintain sobriety, or have a positive EtG on day 3 of abstinence, they will be given an additional chance to make the abstinence criteria before being excluded. For smokers, time of the last cigarette will be recorded and used as a covariate in the glutamate/GABA analysis, if necessary.

Procedure for Pre-Study Evaluation:

Subjects will receive all the pre-study assessment over a several day assessment period during the pre-randomization abstinent period (sobriety days 3-7).

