Power has not been calculated for the exploratory genetic analyses. The genetic SNP's we have chosen to explore are not only indicated by the literature but also, importantly, have a reasonable genotypic distribution. Given our past work and HapMap data (see Preliminary Data section) we expect the distribution of both the *GABRA2* and *GM8* allele frequencies to be about 60:40 with not much difference between Euro-Caucasians and African Americans. This should provide a good balance between treatment groups. Modifier effects are likely to be observable if the effect size is moderate to large. In any case, this data will allow more appropriate power calculations for subsequent studies. Effects of genetic variation on brain glutamate/GABA are unknown and completely novel but as a main effect with 90 subjects (even accounting for drop-outs or unusable scans) the power to detect a gene by analyte effect should be sufficient if clinically meaningful.

Data Analysis Plan: *The PSNHDD (with baseline percent heavy drinking days as a covariate) will be analyzed with a multiple logistic regression with indicator coding medication group as the primary independent variable. All hypotheses (primary, secondary) will be assessed with likelihood ratios. Other possible pre-randomization variables, e.g. sex, smoking status, ADS score, pre-randomization CIWA-Ar score, etc. will be evaluated as possible covariates in the final analysis. Missing data (assuming monotonicity) will be imputed as heavy drinking days. In addition, the relapse time-course will be analyzed by GEE techniques for the full treatment X time factorial design. Secondary outcome variables, e.g. other drinking variables, OCDS, POMS, PSQ index, MES and biomarkers (%dCDT and GGT), will be analyzed as either mixed models (SAS PROC MIXED) or in GEE analyses (SAS GENMOD) depending upon the nature of the variable (parametric or categorical).*

Change in glutamate and GABA levels will be analyzed as a mixed model (SAS PROC MIXED) with time as a within subject variable and medication group as between subject variables. Significant interactions will be interpreted with simple effects and main effects will be assessed in the absence of the interaction. If sex and smoking status (reported by some to effect brain GABA levels), or pre-randomization CIWA-Ar score are found to significantly influence glutamate or GABA levels, or if their inclusion reduces residual variance, they will be included in the model as covariates.

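### Days since last drink at the baseline scan is not a named covariate in the glutamate/GABA model, which gives up some precision and leaves the mediation analysis open to confounding

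*Combined protocol and SAP*

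**What the plan says.** All references are to the combined protocol and SAP.

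- **General Design of the Study** (Approach): treatment starts "After a minimum of 3 and maximum of 7 days of abstinence". The screening text places the baseline scan immediately before the first dose, so the scan has the same 3-to-7-day spread.
- **Screening text after the exclusion criteria**: the dry period was to be "not too long (no longer than 7 days) as to effect potential gabapentin efficacy measurement and/or GABA/glutamate levels". For smokers, "time of the last cigarette will be recorded and used as a covariate in the glutamate/GABA analysis, if necessary".
- **Inclusion Criteria**: "Must be able to maintain sobriety for a minimum of 3 days as determined by self-report, urinary EtG, and breathalyzer measurements". This is an eligibility check.
- **Preliminary Data Supporting Significance**, imaging background: among the factors that might influence 1H-MRS findings, the first listed is "timing of measurement in relationship to alcohol use and abstinence". The same text reports that several studies saw change during early abstinence. It adds that the acamprosate study later used for the glutamate power calculation found glutamate rising in that period.
- **Dosing and Randomization Schedule**: the balancing factors are withdrawal history, sex and smoking status.
- **Data Analysis Plan**, glutamate and GABA: the covariate sentence opens "If sex and smoking status (reported by some to effect brain GABA levels), or pre-randomization CIWA-Ar score" and names no other candidate. The imaging methods add the gray-matter ratio.
- **Data Analysis Plan**, mediation: neurochemical difference scores are entered into the main logistic model, followed by path analysis. No abstinence term is named.

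**The concern.** If glutamate or GABA is still moving in the first week without alcohol, a scan on day 3 and a scan on day 7 sit at different points of that movement. The change from baseline to week 3 then contains a part that reflects only when the first scan took place. The plan handles other items on its own list of influences: sex and smoking by urn randomization and candidate covariates, benzodiazepines by exclusion, brain region by a fixed voxel. It also provides for time since last cigarette. Abstinence timing is limited by the window but not modelled within it.

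Two things are at stake. In the randomized comparison, an explainable source of variation stays in the error term, and a chance difference in scan day between two arms of 45 stays in the estimate. In the mediation analysis the exposure of interest is neurochemical change, which is not randomized. If abstinence length is related both to that change and to relapse, it confounds the association, and randomization to gabapentin gives no protection.

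**Working it through.** **1. The plan's own figures.** Inputs from Outcome Variables and Power Analyses: 45 per arm, d = .95 (power above .99), d = .6 (power .8), at most 10% unusable scans. Alpha is not stated; .05 two-sided is assumed.

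- Noncentrality = d × √(45/2) = d × 4.743.
- d = .6 gives 2.85: power .804 by the t distribution (.812 by the normal).
- d = .95 gives 4.51: power .994.
- Smallest d with 80% power: .597.

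The plan's figures are reproduced.

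**2. Gain from adjustment.** Let r be the correlation of days abstinent with the change score. The documents give no value, so a range is assumed. Adjustment removes r² of the variance, so the effective effect size is d/√(1 − r²). The degree of freedom spent is ignored.

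| assumed r | .6/√(1 − r²) | power, 45/arm | power, 40/arm | smallest d at 80% power, 45/arm |
|---|---|---|---|---|
| 0 | .600 | .804 | .755 | .597 |
| .1 | .603 | .808 | .759 | .594 |
| .2 | .612 | .819 | .772 | .585 |
| .3 | .629 | .839 | .793 | .570 |
| .4 | .655 | .867 | .824 | .547 |

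The 40-per-arm column approximates the plan's 10% scan loss. At d = .95 with 45 per arm, power goes from .994 to .998 at r = .4.

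**3. Chance imbalance.** If days 3 to 7 are equally likely (assumed), the SD is 1.41 days. The standard error of the arm difference is 1.41 × √(2/45) = 0.30 day, so the 95% range is ±0.58 day. With half the subjects at day 3 and half at day 7, the SD is 2.0 and the range ±0.83 day. In SD units of the change score, the 95% range of the shift is r × 1.96 × √(2/45): ±.04 at r = .1, ±.12 at r = .3, ±.17 at r = .4. The detectable effect is .6 SD.

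**4. Error rate without adjustment.** In 20,000 simulated null trials (days equally likely, 45 per arm), the unadjusted test rejected in .048 at r = .3 and .049 at r = .5. Among the 10% of randomizations with the largest imbalance in days, it rejected in about .09 and .14.

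**5. How the covariate must enter.** The model has time as a within-subject factor, and the drug effect on change is the group-by-time term. With both scans present, that term is the arm difference in (week 3 − baseline). A covariate entered only as a main effect adds the same amount b·X to both scans and cancels from the difference. It would leave the estimate essentially unchanged. Only X × time, or X in a model for the change score or the week-3 value, yields the gains in step 2.

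**The case against.** The strongest reply is that the window is itself the control. The screening sentence explains why sobriety is capped at 7 days, and a 3-to-7-day span is narrow. A reader might take that sentence as an admission that variation inside the window affects both efficacy and neurochemistry. It is not: it speaks of a potential effect, joins the two with and/or, and concerns periods that are too long. The firmer support is the imaging background, and that gives no rate of change within days 3 to 7.

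Three further readings go beyond the text.

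- **Every model omits it.** The primary model starts from "The PSNHDD (with baseline percent heavy drinking days as a covariate) will be analyzed with a multiple logistic regression" and then gives an open-ended list of further candidates. General Assessment also allows covariate analysis for chance imbalance. Those provisions answer most of the worry for the primary outcome. They are discretionary, however, and the neurochemical list is specific.
- **Days abstinent is already recorded.** Abstinence is verified for eligibility; the timing variable expressly recorded is the last cigarette. Days since last drink should be derivable from Form 90 and self-report, but that is an inference.
- **The baseline heavy-drinking covariate is distorted by scheduling.** The documents do not define its look-back window, so no such shift can be shown.

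It can also be said that pre-randomization CIWA-Ar stands in for abstinence timing. It may do so in part, but it measures symptoms, is restricted to scores below 10, and enters only conditionally. Finally, the gain rests on an assumed correlation and disappears at d = .95. That is correct, and it limits the size of the point.

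**Conclusion.** The point holds as a minor one for the glutamate, GABA and mediation analyses. The plan treats abstinence timing as a possible influence on 1H-MRS results, lets it vary over five calendar days at baseline, and does not name it in the model for those results.

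A reader might infer that the omission biases the drug comparison. It does not: the value is fixed before randomization, and the overall type I error stays near .05. The cost is precision, together with a chance shift that matters mainly in the more imbalanced randomizations. Under an assumed r of .1 to .4 and two-sided alpha of .05, the power forgone at d = .6 with 45 per arm is between .4 and 6.3 percentage points (.804 against .808 to .867). At d = .95 nothing material is lost. The possible confounding in the mediation analysis cannot be sized from the documents, but it is the part that randomization does not cover.

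**What to change.** 1. Define days from last drink to first scan, derived from Form 90 and self-report, and state that it will be held as an analysis variable.
2. Pre-specify it in the glutamate and GABA models with its interaction with time. Alternatively, make it a covariate in an analysis of the change score or of the week-3 value. A main effect alone is not enough.
3. Pre-specify it as a covariate in the mediation analysis, both in the equation for neurochemical change and in the equation for drinking outcome.
4. For the primary outcome, use it at most as a sensitivity covariate; the existing covariate provisions are otherwise adequate on this point.

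The cost is one or two degrees of freedom per model and a few sentences in the Data Analysis Plan. No extra visit or assay should be needed, provided the date of last drink can be recovered as expected. The abstinence window itself need not change for this purpose.
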